### 7.1.2 Prohibited or Restricted Therapies

The following therapies are prohibited while the subject is on study treatment:

- any investigational agent or investigational medical device
- any drug or herbal product used specifically for the treatment of HCC
- therapeutic doses of oral anticoagulants (eg, warfarin or warfarin-related agents, thrombin or FXa inhibitors, antiplatelet agents such as clopidogrel)
- interferon treatment

Liver-directed local anti-cancer therapy (eg, transarterial tumor embolization or chemoembolization, radiofrequency or microwave ablation, percutaneous ethanol or acetic acid ablation, injection or infusion of drug eluting or radiation-emitting beads, cryoablation, radiation therapy [including stereotactic radiotherapy], or surgery) or systemic anticancer therapies are not permitted on study treatment. If a subject requires additional systemic anticancer treatment or liver-directed local anti-cancer therapy, study treatment must be discontinued. Palliative external radiation to bone metastasis or skin/subcutaneous metastasis, is allowed but discouraged unless medically unavoidable. Subjects who have such intervention may be considered inevaluable for certain efficacy endpoints.

Erythropoietic-stimulating agents (eg, epoetin alfa and darbepoetin alfa) should not be used based on a report of increased risk of tumor recurrence/progression associated with erythropoietin (Wright 2007).

The chronic co-administration of strong CYP3A4 inducers should be avoided (Section 7.1.2.1). Other drugs that induce CYP3A4 should be used with caution because these drugs have the potential to decrease exposure (AUC) to cabozantinib. Selection of alternate concomitant medications with no or minimal CYP3A4 enzyme induction potential is recommended.

Caution must be used when discontinuing treatment with a strong CYP3A4 inducer in a subject who has been concurrently receiving a stable dose of cabozantinib, as this could significantly increase the exposure to cabozantinib.

Coadministration of strong CYP3A4 inhibitors and other drugs that inhibit CYP3A4 should be avoided because these drugs have the potential to increase exposure (AUC) to cabozantinib (Section 7.1.2.1). Selection of alternate concomitant medications with no or minimal CYP3A4 enzyme inhibition potential is recommended.

Additional information on potential drug interactions with cabozantinib is provided in Section 7.1.2.1.

#### **7.1.2.1 Potential Drug Interactions with Cabozantinib**

Cytochrome P450: Data from a clinical drug interaction study (Study XL184-008) show that clinically relevant steady-state concentrations of cabozantinib appear to have no marked effect on the AUC of co-administered rosiglitazone, a CYP2C8 substrate. Therefore, cabozantinib is not anticipated to markedly inhibit CYP2C8 in the clinic, and by inference, is not anticipated to markedly inhibit other CYP450 isozymes that have lower [I]/Ki values compared with CYP2C8

(ie, CYP2C9, CYP2C19, CYP2D6, CYP1A2, and CYP3A4). In vitro data indicate that cabozantinib is unlikely to induce cytochrome P450 enzymes, except for possible induction of CYP1A1 at high cabozantinib concentrations (30  $\mu$ M).

Cabozantinib is a CYP3A4 substrate and a weak substrate for CYP2C9 (but not a CYP2D6, CYP2C8, CYP2C19, CYP2B6, or CYP1A2 substrate), based on data from in vitro studies. Results from a clinical pharmacology study, XL184-006, showed that concurrent administration of cabozantinib with the strong CYP3A4 inducer, rifampin, resulted in an approximately 77% reduction in cabozantinib exposure (AUC values) after a single dose of cabozantinib in healthy volunteers. Co-administration of cabozantinib with strong inducers of the CYP3A4 family (eg, dexamethasone, phenytoin, carbamazepine, rifampin, rifabutin, rifapentin, phenobarbital, and St. John's Wort) may significantly decrease cabozantinib concentrations. The chronic use of strong CYP3A4 inducers should be avoided. Other drugs that induce CYP3A4 should be used with caution because these drugs have the potential to decrease exposure (AUC) to cabozantinib. Selection of alternate concomitant medications with no or minimal CYP3A4 enzyme induction potential is recommended.

Caution must be used when discontinuing treatment with a strong CYP3A4 inducer in a subject who has been concurrently receiving a stable dose of cabozantinib, as this could significantly increase the exposure to cabozantinib.

Results from a clinical pharmacology study, XL184-007, showed that concurrent administration of cabozantinib with the strong CYP3A4 inhibitor, ketoconazole, resulted in a 38% increase in the cabozantinib exposure (AUC values) after a single dose of cabozantinib in healthy volunteers. Co-administration of cabozantinib with strong inhibitors of the CYP3A4 family (eg, boceprevir, conivaptan, posaconazole, ketoconazole, itraconazole, clarithromycin, atazanavir, indinavir, nefazodone, nelfinavir, saquinavir, ritonavir, lopinavir, telaprevir, telithromycin, and voriconazole) may increase cabozantinib concentrations. Grapefruit and Seville oranges may also increase plasma concentrations of cabozantinib. Strong CYP3A4 inhibitors and other drugs that inhibit CYP3A4 should be avoided because these drugs have the potential to increase exposure (AUC) to cabozantinib. Selection of alternate concomitant medications with no or minimal CYP3A4 enzyme inhibition potential is recommended.

Please refer to the Flockhart drug interaction tables and FDA websites for lists of substrates, inducers, and inhibitors of selected CYP450 isozyme pathways (see <http://medicine.iupui.edu/clinpharm/ddis/table.aspx>)

and

<http://www.fda.gov/Drugs/DevelopmentApprovalProcess/DevelopmentResources/DrugInteractionsLabeling/ucm080499.htm> ).

**Protein Binding:** Cabozantinib is highly bound (approximately 99.9%) to human plasma proteins. Therefore, highly protein bound drugs should be used with caution with cabozantinib because there is a potential displacement interaction that could increase free concentrations of cabozantinib and/or a co-administered highly protein-bound drug (and a corresponding increase in pharmacologic effect). Factors that influence plasma protein binding may affect individual tolerance to cabozantinib. Therefore, concomitant medications that are highly protein bound (eg, diazepam, furosemide, dicloxacillin, and propranolol) should be used with caution. Because warfarin is a highly protein bound drug with a low therapeutic index, administration of oral anticoagulants at therapeutic doses is not allowed in subjects receiving cabozantinib due to the potential for a protein binding displacement interaction.

**Other Interactions:** As food increases exposure levels of cabozantinib, fasting recommendations should be followed (Section 6.1). In vitro data suggest that cabozantinib is unlikely to be a substrate for P-glycoprotein, but it does appear to have the potential to inhibit the P-glycoprotein transport activity. Additional details related to these overall conclusions can be found in the investigator brochure.

Administration of the proton pump inhibitor (PPI) esomeprazole resulted in no clinically-relevant effect on cabozantinib plasma PK in healthy volunteers. Therefore, concomitant use of gastric pH modifying agents (ie, PPIs, H2 receptor antagonists, and antacids) is not contraindicated in subjects administered cabozantinib. (**Note:** Cimetidine should be avoided because of its potential to interfere with CYP3A4 mediated metabolism of cabozantinib).

**Drugs that prolong QTc interval:** Drugs known to prolong QTc interval should be avoided.

Additional details regarding potential drug interactions with cabozantinib can be found in the investigator brochure.

## 8 SAFETY

### 8.1 Adverse Events and Laboratory Abnormalities

An AE is any untoward medical occurrence in a patient or clinical investigation subject who has been enrolled in a clinical study and who may have been administered an investigational product, regardless of whether or not the event is assessed as related to the study treatment. An AE can therefore be any unfavorable and unintended sign (including an abnormal laboratory finding), symptom, or disease temporally associated with the use of an investigational product, regardless of whether or not the event is assessed as related to the investigational product. This definition also includes events associated with medication errors and uses of the investigational product outside of what is in the protocol, including misuse and abuse. Preexisting medical conditions that worsen during a study should be recorded as AEs. Abnormal laboratory values, ECG findings, or vital signs are to be recorded as AEs if they meet the criteria described in Section 8.3.

All untoward events that occur after informed consent through 30 days after the date of the decision to discontinue study treatment are to be recorded by the investigational site. At each scheduled and unscheduled visit, AEs are to be identified and assessed based upon study procedures, routine and symptom-directed clinical investigations, and subject query/report.

Assessment of the relationship of the AE to the study treatment by the investigator will be based on the following two definitions:

- **Not Related**: An event is assessed as not related to study treatment if it is attributable to another cause and/or if there is no evidence to support a causal relationship.
- **Related**: An event is assessed as related to study treatment when there is a reasonable possibility that the study treatment caused the event. Reasonable possibility means there is evidence to suggest a causal relationship between the drug and the event. This event is called a suspected adverse reaction. A suspected adverse reaction implies a lesser degree of certainty about causality than adverse reaction, which means any adverse event caused by a drug.

### 8.2 Serious Adverse Events

The SAE definition and reporting requirements are in accordance with the ICH Guideline for Clinical Safety Data Management, Definitions and Standards for Expedited Reporting, Topic E2A.

#### 8.2.1 Definitions

An SAE is defined as any untoward medical occurrence that at any dose:

- Results in death.
- Is immediately life-threatening (ie in the opinion of the investigator, the AE places the subject at immediate risk of death; it does not include a reaction that, had it occurred in a more severe form, might have caused death).
- Requires inpatient hospitalization or results in prolongation of an existing hospitalization.
- Results in a persistent or significant incapacity or substantial disruption of the ability to conduct normal life functions.
- Is a congenital anomaly or birth defect.
- Is an important medical event that may not be immediately life-threatening, result in death, or require hospitalization, but may be considered an SAE when, based upon appropriate medical judgment, it jeopardizes the subject or may require medical or surgical intervention to prevent one of the outcomes listed above.

As soon as an investigator becomes aware of an AE that meets the criteria for an SAE, the investigator should document the SAE to the extent that information is available.

These SAEs, regardless of causal relationship, must be reported to the Sponsor or designee immediately (within 24 hours of the investigator's knowledge of the event) by submitting the completed SAE report form and any other pertinent SAE information as indicated on the SAE Reporting form (or in the SAE Reporting form Completion Guidelines) and confirming the report was received. Forms for reporting SAEs and contact information will be provided to the study sites. Significant follow-up information (as defined in the SAE Reporting form Completion Guidelines) must also be reported immediately (within 24 hours of the investigator's awareness of the new information).

Serious adverse events that must be recorded on an SAE Reporting form include the following:

- All SAEs that occur after informed consent and through 30 days after the date of the decision to discontinue study treatment (or the date the subject is deemed to be a screen failure).
- Any SAEs assessed as related to study treatment or study procedures, even if the SAE occurs more than 30 days after the date of the decision to discontinue study treatment.

Serious adverse events that occur after the initiation of study treatment through 30 days after the date of the decision to discontinue study treatment must also be recorded on the AE CRF page.

The minimum information required for SAE reporting includes identity of investigator, site number, subject number, an event description, SAE term(s), the reason why the event is considered to be serious (ie, the seriousness criteria) and the investigator's assessment of the relationship of the event to study treatment. Additional SAE information including medications

or other therapeutic measures used to treat the event, action taken with the study treatment because of the event, and the outcome/resolution of the event will be recorded on the SAE form.

In all cases, the investigator should continue to monitor the clinical situation and report all material facts relating to the progression or outcome of the SAE. Furthermore, the investigator may be required to provide supplementary information as requested by the Exelixis Drug Safety personnel or designee.

When reporting SAEs, the following additional points should be noted:

- When the diagnosis of an SAE is known or suspected, the investigator should report the diagnosis or syndrome as the primary SAE term, rather than as signs or symptoms. Signs and symptoms may then be described in the event description.
- Death should not be reported as an SAE, but as an outcome of a specific SAE, unless the event preceding the death is unknown. Terms of “Unexplained Death” or “Death from unknown origin” may be used when the cause is unknown. In these circumstances the cause of death must be investigated and the diagnosis amended when etiology identified. If an autopsy was performed, the autopsy report should be provided.
- While most hospitalizations necessitate reporting of an SAE, some hospitalizations do not require SAE reporting, as follows:
  - Elective or previously scheduled surgeries or procedures for preexisting conditions that have not worsened after initiation of treatment (eg, a previously scheduled ventral hernia repair). SAEs must, however, be reported for any surgical or procedural complication resulting in prolongation of the hospitalization.
  - Pre-specified study hospitalizations for observation.
  - Events that result in hospital stays of fewer than 24 hours and that do not require admission (eg, an emergency room visit for hematuria that results in a diagnosis of cystitis and discharge to home on oral antibiotics).
- SAEs must be reported for any surgical or procedural complication resulting in prolongation of the hospitalization.

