### **15.4 Case Report Forms**

The term "case report form" includes, as applicable, paper forms, electronic data capture screens or forms for studies that utilize electronic data capture. For randomized subjects, all and only data for the procedures and assessments specified in this protocol and required by the case report

forms should be submitted on the appropriate CRF (unless transmitted to the Sponsor or a designee electronically, eg, central laboratory data). Data from some procedures required by the protocol, such as physical exams, will be recorded only on the source documents. Additional procedures and assessments may be performed as part of the investigator's institution or medical practice standard of care. Data from assessments associated with the follow-up of AEs should be recorded on unscheduled CRF pages. Otherwise, data for unscheduled or additional assessments should remain in the subject's medical record and should not be recorded on CRFs unless specifically requested.

The CRF (paper or electronic) must be completed and signed by the investigator or authorized delegate from the study staff. This also applies to records for those subjects who fail to complete the study or are randomized and never treated. If a subject stops dosing or terminates from the study, the dates and reasons must be noted on the CRF.

All paper forms should be typed or filled out using indelible ink and must be legible. Errors should be crossed out but not obliterated, the correction inserted, and the change initialed and dated by the investigator or his or her authorized delegate. The investigator should ensure the accuracy, completeness, legibility, and timeliness of the data reported to the Sponsor in the CRF and in all required reports.

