#### 8.1 Adverse Events

Adverse event terms recorded on the CRF will be mapped to preferred terms and system organ class using the Medical Dictionary for Regulatory Activities (MedDRA). The severity of AEs will be measured by CTCAE (Cancer Therapy Evaluation Program 2009) version 4 guidelines. The investigator will judge each event to be "not related" or "related" to study treatment.

A TEAE is defined as any event with an onset date on or after the date of the first dose of study drug or any ongoing event on the date of the first dose of study drug that worsens in severity after the date of the first dose of study drug.

Only TEAEs with an onset date through the end of the safety observation period (see section 4.5) will be tabulated in summary tables.

For the purpose of calculating treatment emergence and inclusion in summary tables, incomplete onset dates will be imputed as detailed in Appendix A.

For AE reporting, percentages  $\geq 10\%$  will generally be presented as integers, those  $\leq 10\%$ 

will be presented with 1 decimal place (e.g. X.X%). Rounding rules are provided in Appendix B. The calculations of percentages will be based on original unrounded values.

An overall summary of adverse events will be provided with the number and percent of subjects who experienced the following types of events during the safety observation period (unless otherwise noted) in each treatment arm:

- Subjects with a TEAE
- Subjects with a Related TEAE
- Subjects with a Serious TEAE
- Subjects with a Serious Related TEAE at any time
- Subjects with a Worst-Grade 3 or 4 TEAE
- Subjects with a Worst-Grade 3 or 4 Related TEAE
- Subjects with a Worst-Grade 4 TEAE
- Subjects with a Worst-Grade 4 Related TEAE
- Subjects with a Grade 5 TEAE at any time
- Subjects with a Grade 5 TEAE
- Subjects with a Grade 5 TEAE through 30 days after the last dose of the study treatment
- Subjects with a Grade 5 AE judged not to be causally related to PD through 30 days of last dose of the study treatment
- Subjects with a Grade 5 AE >30 days after the last dose of the study treatment
- Subjects with a Grade 5 AE judged not to be causally related to PD >30 days of last dose of the study treatment
- Subjects with a Related Grade 5 TEAE at any time
- Subjects with a Related Grade 5 TEAE
- All subjects who died
- Subjects who died within 30 days after date of last dose of study treatment
- Subjects with a TEAE leading to Dose Modification

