# 8.2 Deaths

All reported subject deaths and whether death was causally associated with the disease under study (HCC) will be summarized by treatment arm for all subjects in the Safety population. The primary cause of death recorded on the CRF will be mapped to preferred term and system organ class using MedDRA. The coded terms will be merged with AE records to determine the relationship to study treatment.

Deaths will be summarized in 2 main categories as follows:

- Deaths within 30 days after the date of receipt of the last dose of study treatment
- Deaths greater than 30 days after the date of receipt of last dose of study treatment

Summary of primary cause of death will be tabulated under each category by causality to study disease and relationship to study drug.

All reported subject deaths will be listed.

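### Related SAEs that start more than 30 days after the decision to stop treatment are not required on the AE CRF page, so the SAP's late-event rows, built from CRF terms, can be incomplete

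*Protocol*

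**What the plan says.** Protocol 8.2.1 sets two windows close together. The SAE Reporting form takes every SAE up to 30 days after the decision to discontinue and, beyond that, "Any SAEs assessed as related to study treatment or study procedures, even if the SAE occurs more than 30 days after the date" of that decision. The AE CRF page has a limit: SAEs from the start of treatment "through 30 days after the date of the decision to discontinue study treatment must also be recorded on the AE CRF page". Protocol 8.1 puts the same end date on what sites record as adverse events in general: "All untoward events that occur after informed consent through 30 days after the date of the decision to discontinue study treatment". Protocol 15.4 tells sites to submit on the CRF "all and only data for the procedures and assessments specified in this protocol" and required by the forms.

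SAP 8.1 names its source: "Adverse event terms recorded on the CRF will be mapped to preferred terms and system organ class". Its overview is limited to the safety observation period unless a row says otherwise, and several rows do. They include "Subjects with a Serious Related TEAE at any time", matching any-time rows for Grade 5 and related Grade 5 events, and "Subjects with a Grade 5 AE >30 days after the last dose of the study treatment". There is a further row for late Grade 5 events judged not due to progression, and separate Grade 5 tables for the period after 30 days.

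SAP 8.2 splits deaths at 30 days after last dose and tabulates both groups by relationship to study drug. On how that relationship is found, it says: "The coded terms will be merged with AE records to determine the relationship to study treatment".

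**The concern.** The any-time and after-30-days rows are there to show harm that appears after the usual safety window. They need events that the protocol sends to the SAE form but does not require on the form the tables are built from. Neither document says that SAE-form or safety-database records are added to the CRF data for these rows. The safety database is named as a source of summaries only for the Maintenance Phase (Protocol 9.11).

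A reader of the study report would take these rows as full counts of late serious and fatal related events, and would have no sign that the data flow had cut them short. The same applies to the relationship column for late deaths, which Protocol 9.7.1 also promises.

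**Working it through.** The documents state no figure to reproduce. The check sets the collection rules beside the rows that depend on them.

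**One event traced through the rules.** Take the decision to discontinue as day 0 and a related SAE starting on day 31.

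1. SAE Reporting form (Protocol 8.2.1): required, because the event is related.
2. AE CRF page (Protocol 8.1 and 8.2.1): not required, since 31 > 30.
3. Follow-up (Protocol 8.3.4): required until it resolves, improves or stabilises, but with no instruction to enter the event on the AE page.
4. SAP 8.1: a table of CRF terms has no required record to count.
5. If the event is fatal, Protocol 5.5.2 still collects the date and cause of death. It does not collect relationship to study drug, and the SAP 8.2 merge has no required AE record to match.

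**By type of event**

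| Event | SAE form | AE CRF page | SAP rows affected |
|---|---|---|---|
| Related SAE starting by day 30 | Required | Required | None |
| Starts by day 30, fatal later | Required | Required | Can be counted and matched |
| Related SAE starting after day 30, not fatal | Required | Not required | Serious related, any time |
| Related SAE starting after day 30, fatal | Required | Not required | As above, plus the any-time and late Grade 5 rows and the relationship of late deaths |
| Unrelated fatal event starting after day 30 | Not required | Not required | General Grade 5 rows (any time and late) |

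**Why the late rows are not empty.** They count from last dose, while collection counts from the decision date. Protocol 6.5.1 allows interruptions of up to 6 weeks. If treatment is held for 42 days and then stopped, the CRF window reaches 42 + 30 = 72 days after last dose. An event between day 31 and day 72 after last dose is then both recorded and counted as late.

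**Size.** The documents give no rate of late related SAEs. As an illustration only, assume 0.5% to 2% of the 507 planned cabozantinib subjects (Protocol 9.9):

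- 0.005 × 507 = 2.5, about 3 subjects
- 0.02 × 507 = 10.1, about 10 subjects

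**The case against.** The strongest reply is that Protocol 8.2.1 sets a minimum. It says what must go on the AE page and does not bar later entries. The CRF itself and the SAE form completion guidelines are not part of these documents, and the SAP's any-time rows may have been written for a dataset that holds late related SAEs. Protocol 15.4 also sends data from the follow-up of adverse events to unscheduled CRF pages, and Protocol 8.3.4 requires such follow-up for late related SAEs. This stands against a reading that late related SAEs can exist only on the SAE form. It does not close the gap: the unscheduled pages are not said to be the AE page, and no text sends a new late event there.

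A reader might infer that the any-time rows simply repeat the windowed ones, or that every late death would appear unrelated. The documents do not support that. An event that starts inside the window and later proves fatal has an AE record and can be matched. The offset between last dose and decision date lets in others.

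A reader might also infer that most late deaths are lost, since many deaths will come after treatment ends. They are not: date and cause are collected until death (Protocol 5.5.2), and SAP 8.2 summarises and lists all of them. Only the relationship is at risk, and only for late deaths that are related and lack a matching AE record.

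New related events may also be few. With a terminal half-life of about 99 to 120 hours (Protocol 1.3.3.4), 30 days is 720/120 = 6 to 720/99 = 7.3 half-lives. That bears on the number. Even so, the protocol chose to collect such events and the SAP chose to report them.

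Finally, late related SAEs still reach the sponsor within 24 hours of the investigator's knowledge and are assessed for expedited reporting. The weakness is in the analysis tables, not in safety reporting.

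**Conclusion.** The concern holds as a mismatch between collection and analysis. As written, the rows for serious related and Grade 5 events at any time, and for Grade 5 events after 30 days, are incomplete for related SAEs that start after the collection window. A related death after that window cannot be shown as related unless a matching AE record began within it.

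The number affected cannot be derived from the documents. The 3 to 10 subjects above rest wholly on an assumed rate. Nor do the documents show which types of event, or which arm, would carry the shortfall.

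The general Grade 5 rows have a wider gap, because unrelated fatal events after the window are required on neither form.

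The safety summaries are descriptive, and no efficacy result or stopping boundary depends on these rows. The conclusion assumes that no CRF instruction or reconciliation rule outside these documents already fills the gap. If one does, a sentence in the SAP citing it is enough. The change is worth making because the rows exist to show late related harm and would be read as complete.

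**What to change.** Do one of the following for related events:

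- In Protocol 8.2.1, require any SAE assessed as related to study treatment to be entered on the AE CRF page regardless of when it occurs, with a matching note in the CRF instructions; or
- In SAP 8.1 and 8.2, state that the any-time and after-30-days related rows, and the relationship of late deaths, include SAE-form (safety database) records reconciled with the clinical database before lock.

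Neither change completes the general Grade 5 rows. For those, take late deaths from the cause-of-death data in survival follow-up, or add a footnote that unrelated fatal events more than 30 days after the decision to discontinue are not collected as adverse events. It would also help to say whether the late rows are dated by onset or by death.

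The cost is a sentence or two, a few extra AE records for events that sites already report on the SAE form, and a reconciliation step.
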